3.7.2 Adverse Events of Special Interest

Adverse events of special interest (AESI) will include targeted AEs of hypersensitivity (including anaphylaxis), thrombocytopenia, and immune complex disease (eg, vasculitis, endocarditis, neuritis, glomerulonephritis), and the type, incidence, and relationship to study investigational product will be summarized by treatment group and by SOC and PT based on MedDRA. Additional groupings may be added by the Medical Monitor, if warranted.

3.7.3 Skin and Hypersensitivity Reactions

All skin reactions and skin reactions identified as hypersensitivity/allergic reactions and the type, incidence, and relationship to study investigational product will be summarized by treatment group, and by SOC and PT based on MedDRA.

3.7.4 New Onset Chronic Disease

New onset chronic diseases include, but are not limited to diabetes, autoimmune disease (eg, lupus, rheumatoid arthritis), and neurological disease (eg, epilepsy) and the type, incidence, and relationship to study investigational product will be summarized by treatment group and by SOC and PT based on MedDRA.

3.7.5 Subgroup Analyses

All AEs will be summarized by age group used as randomization stratum (age \leq 3 months, age $>$ 3 to \leq 6 months), weight on Day 1 (weight \leq 2.5 kg, weight $>$ 2.5 to \leq 5 kg, weight $>$ 5 kg), and age at randomization by \leq 8 months or $>$ 8 months. In addition, TEAEs occurring within 1-day and 7-day post dose by age at randomization (\leq 3 Months, $>$ 3 to \leq 6 Months, $>$ 6 Months) will also be summarized, respectively.

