2.2 Study Design

The population to be enrolled is healthy preterm infants born between 29 weeks 0 days and 34 weeks 6 days GA who would not receive RSV prophylaxis based on the American Academy of Pediatrics (AAP) or other local or national guidelines. These infants will not be receiving palivizumab, allowing for a placebo comparator group for the determination of efficacy and the safety profile. A total of 1,500 infants will be randomized in a 2:1 ratio to receive a 50 mg IM dose of MEDI8897 (N = 1000) or placebo (N = 500). Randomization will be stratified by temperate zones in the northern and southern hemisphere and by subject age group at randomization (ie, ≤ 3 months, > 3 to ≤ 6 months, > 6 months). Enrollment of infants > 6 months of age will be limited to approximately 500. All infants will be followed for approximately 360 days after dosing.

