3.3 Stratification Factors

Two stratification factors are used in study design as well as in data analysis, and these are: age group at randomization [age \leq 3 months (ie, age \leq 91 days), age $>$ 3 to \leq 6 months (ie, age $>$ 91 to \leq 183 days), age $>$ 6 months (ie, age $>$ 183 days)] and hemisphere (northern hemisphere, southern hemisphere). For subjects who were assigned to an incorrect age stratum at randomization, the age stratum as calculated from the electronic case report form (eCRF) will differ from the stratum recorded for the subject in the IWRS database. Unless stated otherwise, the age stratum based on the CRF calculation will be used.

CRF calculation for age when full date of birth (DOB) is available:

- Age at randomization (months) = (randomization date – DOB) / (365.25/12)

When full DOB is unavailable, age at screening will be used. Since screening may be collected in terms of days, weeks, or months, it will be first converted in terms of months as follows:

- Age at screening (days) / (365.25/12) = Age at screening (months)
- Age at screening (weeks) / (52/12) = Age at screening (months)

Once age at screening is converted to months,

- Age at randomization (months) = Age at screening (months) + [(randomization date – screening date) / (365.25/12)]

Determination of hemisphere in stratification and analysis is as follows: The sites have been grouped together by country into the following two hemispheres: Northern Hemisphere (Belgium, Bulgaria, Canada, Czech Republic, Estonia, Finland, France, Hungary, Italy, Latvia, Lithuania, Poland, Spain, Sweden, Turkey, United Kingdom, and United States of America [USA]) and Southern Hemisphere (Argentina, Australia, Brazil, Chile, New Zealand, and South Africa).

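### SAP v5 section 3.7.5 names only two of the three randomization age strata for the all-adverse-event summary, so infants over 6 months get no column of their own over full follow-up

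*SAP*

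**What the plan says.** The operative sentence is the first in SAP v5 section 3.7.5 (safety subgroup analyses): "All AEs will be summarized by age group used as randomization stratum". The bracketed list after these words names infants up to 3 months and infants over 3 and up to 6 months, and the bracket closes after the second age level. The same sentence also plans the all-event summary by three Day 1 weight groups and by age at randomization cut at 8 months.

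The next sentence adds a summary of "TEAEs occurring within 1-day and 7-day post dose by age at randomization" and gives three age levels for it, including over 6 months.

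Elsewhere in the same SAP version the stratum has three levels. Section 2.2 stratifies by "subject age group at randomization (ie, ≤ 3 months, > 3 to ≤ 6 months, > 6 months" and adds that "Enrollment of infants > 6 months of age will be limited to approximately 500". Section 2.3 repeats both statements. Section 3.3 defines the third level as age above 183 days. The efficacy subgroup list in section 3.5.1.7 uses all three. Section 3.7 places all safety analyses on the As-treated population.

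**The concern.** The sentence refers to the randomization stratum and then omits one of its levels. Protocol section 5.5.1 has adverse events collected through the Day 361 visit. The all-event summary by stratum is the only planned table that would show events over that whole period separately for each randomization age group.

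A programmer who follows the list gives no column to a stratum that has its own enrollment limit, and the columns do not add up to the safety population. A programmer who adds the column departs from the signed text. Either way, someone reading the clinical study report could not tell whether the missing group was a choice or a slip.

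**Working it through.** The SAP states no figure to reproduce here. The check compares the texts and then sizes the gap.

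**Step 1. Age levels named in SAP v5.**

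| Place | ≤ 3 mo | > 3 to ≤ 6 mo | > 6 mo |
|---|---|---|---|
| 2.2 and 2.3, randomization | yes | yes | yes |
| 3.3, stratum definition | yes | yes | yes (> 183 days) |
| 3.5.1.7, efficacy subgroups | yes | yes | yes |
| 3.7.5, second sentence (1-day and 7-day events) | yes | yes | yes |
| 3.7.5, first sentence (all adverse events) | yes | yes | **no** |

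Section 3.7.5 of the superseded SAP version 4 listed all three levels and already had the 8-month split. The 8-month split therefore did not replace the third stratum. The version 5 text gives no reason for dropping it.

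**Step 2. Where infants over 6 months appear in the planned safety output.**

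- Overall treatment-emergent event tables (3.7.1), special-interest events (3.7.2) and new onset chronic disease (3.7.4): included, not shown separately.
- All events by Day 1 weight (3.7.5): included, spread over weight groups.
- All events at ≤ 8 and > 8 months (3.7.5): included. The > 8 months column consists wholly of this stratum but holds only part of it. The rest is in the ≤ 8 months column with the two younger strata.
- Treatment-emergent events within 1 and 7 days by age (3.7.5): own column, early period only.
- Events by timing relative to dosing (3.7.6): included, not split by age.
- All events by randomization stratum (3.7.5): no column as written.

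No full-follow-up table shows the stratum on its own.

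**Step 3. Size.** Inputs are the cap of about 500, the planned total of 1,500 and the 2:1 allocation, all from section 2.2.

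- Share of planned infants if the cap is filled: 500 / 1,500 = 33.3%.
- On MEDI8897: 500 × 2/3 ≈ 333. On placebo: 500 × 1/3 ≈ 167.
- Covered by the two listed strata: 1,500 − 500 = 1,000.
- Section 3.1 gives 722 + 731 = 1,453 subjects. On that total a filled cap is 500 / 1,453 = 34.4%, still about one third.

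The cap limits enrollment and does not predict it, so these figures are ceilings. The documents do not give the stratum's actual size.

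**Step 4. Can the missing column be recovered?** The three strata partition the subjects, and section 3.7.1 counts each specific event once per subject. Within an arm, for any event:

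n(> 6) = n(≤ 8) + n(> 8) − n(≤ 3) − n(> 3 to ≤ 6)

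All four terms on the right come from tables planned in the first sentence of 3.7.5, so they cover the same set of events. The denominators follow in the same way. The count is recoverable exactly; what is missing is its display.

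**The case against.** The strongest reply is that the operative words are the reference to the randomization stratum. Section 3.3 gives that factor three levels and says it is used in both design and analysis. On that reading, three columns are required and the bracket is merely incomplete. The next sentence, with all three levels, supports this. The introduction to the SAP also says that table templates will be set out in a separate programming plan, which may already contain the third column.

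Much of this stands. The omission is most likely a drafting slip, and nothing suggests a deliberate analysis choice. It does not remove the contradiction, because an explicit list of levels invites a literal reading and the programming plan is not part of these documents.

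The step 4 identity also limits the consequence. A reader might infer that the 8-month split cannot help because its lower part mixes all three strata. That is not so: together with the two listed strata, it gives the missing counts exactly.

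A reader might also take the table by age to be the planned check on one fixed dose given across a wide age range. Neither document assigns it that role, and the adverse-event summary by Day 1 weight keeps all three of its levels.

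**Conclusion.** The point holds as an internal inconsistency of minor severity. The first sentence of section 3.7.5 names two of three levels of a factor that SAP v5 otherwise defines and uses with three. Taken literally, it leaves the over-6-months stratum without its own column in the full-follow-up adverse-event table by stratum.

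The size is at most about one third of infants. This assumes that the enrollment cap is filled, that the planned totals apply, and that allocation within the stratum is 2:1. It also assumes that the list is followed as written and that the programming plan does not already correct it.

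A reader might conclude that up to a third of infants drop out of safety reporting. The documents do not support that. No subject's events go unreported, as step 2 shows. No hypothesis test, significance level, efficacy estimate or sample size depends on this table.

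**What to change.** In the first sentence of SAP v5 section 3.7.5, add age > 6 months as the third level, so that the list matches section 3.3 and the sentence that follows it. If the omission was intended, say so and give the reason. The programming plan's table template should be checked against the corrected list.

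The cost is a few words and one table column. No new data and no other analysis are involved.

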3.7.6 Other Safety Evaluations

TEAEs, AESIs, skin reactions, and skin hypersensitivity reactions will also be summarized by timing relative to dosing ('within 1 day/greater than 1 day,' 'within 7 days/greater than 7 days').

Additional data collected throughout the study include screen failure data, significant findings in medical history and physical exam, vital signs, and concomitant medications through Day 361. Data listings will be provided and no formal analyses will be conducted on these data. Upon review of the listings, additional summary tables may be generated as appropriate.

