5.3.2 Immune Complex Disease

Immune complex disease can manifest in the form of a number of conditions such as vasculitis, endocarditis, neuritis, glomerulonephritis, serum sickness, and arthralgias. Drug-induced immune complex (type III) hypersensitivity reactions can occur when host immune system generates antibodies to drug resulting in soluble circulating antigen-antibody complexes formation and their deposition in blood vessels. Subsequently this initiates tissue

damaging inflammatory reactions mediated by complement and/or leukocytes and mast cells. The pathology and clinical manifestations are dependent on the tissues/organs involved, with vascular, skin and renal tissues being common sites of injury. Common examples of immune complex hypersensitivity reactions are serum sickness (systemic) and Arthus reactions (local). The clinical manifestations of serum sickness include skin rash, fever, malaise and polyarthralgias or polyarthritis. Symptoms typically develop 1 to 2 weeks after first exposure to antigen and usually resolve in several weeks after withdrawal of the causative agent. Serum sickness needs to be differentiated from other ‘serum-sickness-like’ reactions that have a similar clinical presentation (eg, viral infections, anti-seizure drugs), but are believed to have different pathogenic mechanisms. Both serum sickness and serum sickness-like reactions have been reported with mAbs (eg, rituximab, infliximab). Clinical presentation and time to onset should be taken into account for the diagnosis and differentiation of these reactions. Diagnosis of these suspected reactions is best confirmed via biopsy of the affected tissues. See Section 5.5 for recording AEs.

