5.7.2 Adverse Events of Special Interest

5.7.2.1 Hypersensitivity, Including Anaphylaxis

Events of hypersensitivity, including anaphylaxis (as defined in [Appendix 3](#)), require that the investigator or other site personnel inform appropriate sponsor study representatives immediately, or **no later than 24 hours** of when he or she becomes aware of the event. The designated sponsor study representative works with the Investigator to ensure that all relevant information is provided and entered in EDC. If the event is considered serious it must be reported as an SAE (see Section [5.6](#)).

Signs of hypersensitivity include urticaria, pruritis, angioedema, skin rash, difficulty breathing, and wheezing. Parent(s)/legal representatives will be provided a card with this information to aid in prompt identification and reporting of these signs. Parent(s)/legal representatives will be instructed to immediately report the occurrence of any of these findings to the site investigator who should then report the events to appropriate sponsor study representatives immediately, or **no later than 24 hours** of when he or she becomes aware of the event.

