- An unreasonable temporal relationship between administration of the investigational product and the onset of the event (eg, the event occurred either before, or too long after, administration of the investigational product for it to be considered product-related)
- A causal relationship between the investigational product and the event is biologically implausible (eg, death as a passenger in an automobile accident)
- A clearly more likely alternative explanation for the event is present (eg, typical adverse reaction to a concomitant drug and/or typical disease-related event)

Individual AE/SAE reports will be considered “related” to use of the investigational product if the “not related” criteria are not met.

“Related” implies that the event is considered to be “associated with the use of the drug” meaning that there is “a reasonable possibility” that the event may have been caused by the product under investigation (ie, there are facts, evidence, or arguments to suggest possible causation).

Relationship to Protocol Procedures

The investigator is also required to provide an assessment of relationship of SAEs to protocol procedures on the eCRF (Section 5.6). This includes nontreatment-emergent SAEs (ie, SAEs that occur prior to the administration of investigational product) as well as treatment-emergent SAEs. A protocol-related SAE may occur as a result of a procedure or intervention required during the study (eg, blood collection, nasal sample collection). The following guidelines should be used by investigators to assess the relationship of SAEs to the protocol:

Protocol related: The event occurred due to a procedure/intervention that was described in the protocol for which there is no alternative etiology present in the subject’s medical record.

Not protocol related: The event is related to an etiology other than the procedure/
intervention that was described in the protocol (the alternative etiology
must be documented in the study subject's medical record).

Appendix 3 National Institute of Allergy and Infectious Diseases (NIAID) and Food and Allergy Anaphylaxis Network (FAAN) Guidance for Anaphylaxis Diagnosis

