1 INTRODUCTION

This document describes the statistical analysis plan (SAP) for protocol D5290C00003, a pivotal Phase 2b study to determine if MEDI8897 is efficacious in reducing medically attended respiratory syncytial virus (RSV)-confirmed lower respiratory tract infection (LRTI) in healthy preterm infants entering their first RSV season. The primary efficacy hypothesis of this study is that, compared with placebo, a single 50-mg intramuscular (IM) dose of MEDI8897 will be efficacious in reducing medically attended LRTI caused by reverse transcriptase-polymerase chain reaction (RT-PCR)-confirmed RSV in healthy preterm infants born between 29 weeks 0 days and 34 weeks 6 days gestational age (GA) and entering their first RSV season, and the safety profile will be acceptable. The secondary hypotheses are that (1) there will be a reduction in the incidence of hospitalizations attributable to RSV, (2) the predicted extended terminal half-life ($t_{1/2}$) will be adequate for the duration of the RSV season, and (3) anti-drug antibodies (ADA) to MEDI8897 will not significantly impact the serum concentrations or safety of MEDI8897 over the 5-month RSV season. These hypotheses will be assessed by the incidence of RSV LRTI, RSV hospitalization, ADA, pharmacokinetic (PK) parameters, and descriptive statistics from safety data. This document details the statistical summaries relating to each study objective and describes the general conventions and definitions that will be used.

In addition, a set of table templates and specifications is planned to be created in a statistical programming plan to complement this document.

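### The safety tables by time since dose cut only at 1 and 7 days, so a week-2 excess recorded as plain fever or unrecognised rash is pooled with about 350 days of background events

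*SAP*

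**What the plan says.** SAP v5 Section 3.7.6 lists four groups of events (TEAEs, AESIs, skin reactions, skin hypersensitivity reactions) and summarises them "by timing relative to dosing ('within 1 day/greater than 1 day,' 'within 7 days/greater than 7" days). Section 3.7.5 adds tables of "TEAEs occurring within 1-day and 7-day post dose by age at randomization", with the same two cuts. The general TEAE, AESI and skin tables (Sections 3.7.1 to 3.7.3) and the tables by ADA status (Section 3.8) state no time window. The only other time cuts for adverse events, at 150 and 360 days, are for events associated with LRTI (Sections 3.5.1.5 and 3.5.3).

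On delayed reactions, Protocol 5.3.2 says of serum sickness: "Symptoms typically develop 1 to 2 weeks after first exposure to antigen". It adds: "The clinical manifestations of serum sickness include skin rash, fever, malaise and polyarthralgias or polyarthritis". Investigators are told: "Clinical presentation and time to onset should be taken into account for the diagnosis and differentiation of these reactions".

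SAP Section 1 says that "a set of table templates and specifications is planned to be created in a statistical programming plan". That plan is not among the documents, so this point concerns the SAP text only.

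**The concern.** The two cuts suit acute reactions. They do not suit the delayed reaction that the protocol itself describes. Dosing is Day 1 (Protocol 4.2.2) and adverse events are collected to the Day 361 visit (Protocol 5.5.1), so the later bin holds week 2 together with nearly a year of ordinary infant illness.

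A case diagnosed as immune complex disease is an AESI with its own summary and loses only its onset detail. The weaker spot is an event that nobody links to the product. Fever is the clearest example. Protocol 5.3.2 names it as a sign of serum sickness, but it is not among the signs on the parent card: "Signs of hypersensitivity include urticaria, pruritis, angioedema, skin rash, difficulty breathing, and wheezing". Under Protocol Appendix 2 an event counts as not related if "A clearly more likely alternative explanation for the event is present", and an infant's fever often has one. For such events a difference between the arms in the right window is a useful sign, and the planned split dilutes it.

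**Working it through.** **Plan's own figure.** The documents give no figure for the timing windows. The only stated safety-detection probability is 90% for at least one event at a true rate of 0.2% in 1,000 infants. The binomial value is 1 - 0.998^1000 = 86.5%. That is a separate small mismatch and is not used here.

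**Length of the bin.** About 360 days after dosing less 7 gives 353 days. Days 8-14 are 7 of these, or 7/353 = 2%. If within 7 days means Days 1-7, all 7 days of week 2 fall in the later bin. If it means up to 7 days after dosing (Day 8), 6 of 7 do. The SAP does not say which. At the Primary Analysis about half of the infants have only about 8 months of follow-up, so the pool is then somewhat shorter.

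**Inputs for the dilution.**
- Arms: 722 + 731 = 1,453 infants (SAP v5 Section 3.1), split 2:1 into 969 and 484.
- Background b over the later bin: assumed at 2, 5, 10, 20 and 40%. The documents give no rash rate. The only infant fever figure is 8/71 on MEDI8897 against 0/18 on placebo, at an interim with varied follow-up (Protocol 1.4). No yearly rate can be derived from it.
- Excess: assumed at 1% of treated infants, all with onset in Days 8-14.

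**Formulas.** Background in a window of d days = 1 - (1 - b)^(d/353), with d = 353 (planned bin), 7 (Days 8-14) or 24 (Days 8-31). Risk on MEDI8897 = 1 - (1 - background)(1 - 0.01). Expected counts are risk times arm size. The chance of a two-sided Fisher p ≤ 0.05 is the exact sum over both binomial distributions.

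**Example, b = 20%.** Planned bin: placebo 484 × 0.200 = 97; MEDI8897 969 × (1 - 0.80 × 0.99) = 969 × 0.208 = 202; relative risk (RR) 1.04. Days 8-14: background 1 - 0.8^(7/353) = 0.44%, placebo 484 × 0.0044 = 2.1; MEDI8897 969 × 0.0144 = 14; RR 3.2.

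| b | Planned bin, MEDI8897 vs placebo | RR | Days 8-14 | Fisher chance: planned bin | Days 8-14 | Days 8-31 |
|---|---|---|---|---|---|---|
| 2% | 29 vs 10 | 1.49 | 10 vs 0.2 | 16% | 59% | 51% |
| 5% | 58 vs 24 | 1.19 | 11 vs 0.5 | 10% | 54% | 41% |
| 10% | 106 vs 48 | 1.09 | 12 vs 1.0 | 7% | 47% | 30% |
| 20% | 202 vs 97 | 1.04 | 14 vs 2.1 | 6% | 37% | 19% |
| 40% | 393 vs 194 | 1.01 | 19 vs 4.9 | 5% | 24% | 12% |

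**Variations.** If the early bin runs to Day 8, 6/7 of the excess stays in the later bin and the planned-bin RRs become 1.42, 1.16, 1.08, 1.03 and 1.01. If half of the excess starts in Days 15-31 instead, Days 8-14 alone gives only 7 to 11%, while Days 8-31 is unchanged. No safety test is planned, so the Fisher chances only indicate how visible a cluster would be.

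**The case against.** The plan has several layers that do not depend on these tables.
- Immune complex disease and hypersensitivity are AESIs, reported within 24 hours (Protocol 5.7.2). Rash is on the parent card.
- Relationship is assessed for every event, related is the default, and SAP 3.7.1 tabulates it by arm.
- Protocol 4.7.2 discourages medication from Day 1 through Day 15 and has parents consult the investigator before giving any. A parent who wants to treat a week-2 fever should therefore call.
- SAP 3.8 tabulates TEAEs and SAEs by ADA status. There is also a Day 8 visit, calls every two weeks and regular DMC review.

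The scenario is also built on assumptions. Protocol 5.3.2 lists rash, fever, malaise and joint symptoms together and does not describe a fever-only form. If only 20% of a 1% excess were recognised, the chance of at least one recognised case among 969 would be 1 - (1 - 0.002)^969 = 86%; at 30% it would be 95%. Finally, the remedy helps least where dilution is worst: 37% and 24% at backgrounds of 20% and 40%.

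Most of this stands, and it is why the point is small. It does not close the gap. The individual-case routes need someone to suspect the event, and the medication rule misses a fever left untreated. The ADA tables have no time window and rest on samples scheduled from Day 91. The option in SAP 3.7.6 to add tables after reviewing listings is tied to screening, history, examination, vital-sign and medication data, not to adverse events.

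Two stronger readings do not hold. A reader might infer that the plan would miss serum sickness. It would not, if the case is recognised, because such a case enters the AESI summary whatever its timing. A reader might also take 8/71 against 0/18 as a fever signal. Fisher's p is 0.35, so it is no evidence of an effect.

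**Conclusion.** The point holds in a limited form. On the SAP text, almost all of week 2, which the protocol's own onset period takes in, is merged with about 350 days of other events in every general safety table that has a time-since-dose cut. The loss is in group-level visibility of an excess recorded only as non-specific fever or unrecognised rash. Under a 1% excess confined to Days 8-14, the relative risk in the planned bin falls from 1.49 to 1.01 as background rises from 2% to 40%, while Days 8-14 alone still shows about a doubling at 40%. These sizes rest on assumed rates, a constant background hazard and one event per infant per window. The improvement is modest for common fever and small in Days 8-14 alone if onset is often later.

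No data are lost, and the window could be tabulated afterwards. The gain is that it would be chosen before unblinding, which makes either a finding or its absence easier to believe. Low priority; no efficacy conclusion is affected.

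**What to change.** In SAP v5 Section 3.7.6, keep the 1-day split. Replace the 7-day split with Days 1-7, Days 8-14, Days 15-31 and after Day 31, and state that the dosing day is Day 1. Apply this to all four listed groups, including skin hypersensitivity reactions; for AESIs it serves as onset detail. Show Days 8-31 combined as well, because the protocol says only that onset is typically at 1 to 2 weeks. The by-age tables in Section 3.7.5 can stay as they are.

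The cost is a change of wording and wider descriptive tables: five columns per arm (four windows and the combined one) in place of two, across the affected tables. Onset dates are already collected. More windows across many preferred terms will also produce more chance differences, so the tables should be labelled descriptive.
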